**Table 1: Drug Adverse Event Terms for Abuse Potential Assessment of CVT-301 Safety Data**

15 Adverse Event Terms From CVT-301 Pre-NDA Meeting Minutes, page 5, FDA Response to Question 4b, Item 5 (October 2016)

Abuse, misuse, withdrawal, dependence, dopamine dysregulation syndrome, hedonistic homeostatic dysregulation, euphoria, high, overdose, diversion, hoarding of medication, neuroleptic malignant syndrome, hyperpyrexia, confusion, rebound

19 Adverse Event Terms From FDA Guidance for Industry: Assessment of Abuse Potential of Drugs (January 2017)

Euphoric mood, elevated mood, feeling abnormal, feeling drunk, feeling of relaxation, dizziness, thinking abnormal, hallucination, inappropriate affect, somnolence, mood disorders and disturbances, psychosis, aggression, confusion, disorientation, drug tolerance, habituation, drug withdrawal syndrome, substance related disorders

41 Adverse Event Terms From Setnik, B. A Consensus List Proposal For Adverse Events Related To Abuse And Dependence Potential (Setnik 2016)

Abnormal behavior, abnormal thinking, agitation, cognition disorder, concentration impaired, concentration loss, confusion and disorientation, confusional state, delirium, delusional disorder unspecified type, detachment, disturbance in attention, elation inappropriate, elevated mood, emotional disorder, euphoria/euphoric mood, exhilaration inappropriate, feeling abnormal, feeling drunk, feeling happy inappropriately, flight of ideas, hallucination(visual and auditory), inappropriate affect, inappropriate, elation, inappropriate, laughter, inappropriate mood, elevation, irritability, memory impairment, mental disorder

**MedDRA Preferred Terms based on the composite list of 73 Adverse Event Terms**

Abnormal behavior, acute psychosis, aggression, agitation, cognitive disorder, confusional state, delirium, delirium tremens, delusional disorder unspecified type, delusional perception, dependence, disorientation, dissociation, disturbance in attention, dizziness, dopamine dysregulation syndrome, drug abuse, drug abuser, drug dependence, drug diversion, drug tolerance, drug withdrawal convulsions, drug withdrawal syndrome, elevated mood, emotional disorder, euphoric mood, feeling abnormal, feeling drunk, feeling of relaxation, flight of ideas, hallucination, hallucination auditory, hallucination gustatory, hallucination mixed, hallucination olfactory, hallucination synanesthetic, hallucination tactile, hallucination visual, hedonistic homeostatic dysregulationa, hyperpyrexia, inappropriate affect, intentional overdose, intentional product misuse, irritability, medication overuse headache, memory impairment, mental disorder, mental impairment, mood altered, mood swings, neuroleptic malignant syndrome, overdose, paranoia, parkinsonism hyperpyrexia syndrome, psychosis, psychotic disorder, reactive psychosis, rebound psychosis, rebound tachycardia, sedation, sensory disturbance, somnolence, stupor, substance abuse, substance abuse psychotic disorder, substance abuser, substance dependence, substance-induced mood disorder, substance-induced psychotic disorder, thinking abnormal, thought withdrawal, withdrawal hypertension, withdrawal syndrome

a There is no MedDRA PT for “hedonistic hemostatic dysregulation” listed in the pre-NDA Meeting Minutes, page 5, FDA Response to Question 4b, Item 5 (October 2016) and it was included in the list of MedDRA PT for completeness.

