10.1.4. Sub-Study to Assess Potential Withdrawal Symptoms

After patients are consented to protocol Version 5.2, they will participate in a withdrawal symptom sub-study at the end of TV4, TV5, or TV6, depending on which of the visits is the next scheduled one for the patient. In addition to the assessments detailed in the previous sections for the treatment visit, the AWQ and DDS-PC will be performed upon arrival in the ON state, and the UPDRS Part 1 will be performed preferably in the ON state.

When study activities for the visit are completed, patients will begin a 28-day period of assessment of potential drug withdrawal symptoms. To this end, patients who are at TV4 or TV5 at the time of consent will go on a study drug holiday for this time period. All patients in the withdrawal sub-study (patients consented to protocol Version 5.2) will be given copies of the AWQ, the DDS-PC, PHQ-9, Epworth Sleepiness Scale, C-SSRS (self-report version), and the self-administered MDS-UPDRS Parts 1B and 2 (Movement Disorder Society -UPDRS) to be completed at home at 1, 3, 6, 8, 11, 14, 17, 24, and 28 days after the treatment visit. Patients should fill out the questionnaires during their first ON state (after the intake of their first scheduled dose of standard oral PD medication) on each of these days. The site will call patients

at 14 (± 3) days after the treatment visit to remind them to complete the questionnaires, and to inquire about potential adverse events and changes in concomitant medications. Patients who enter the withdrawal sub-study after TV6 will also receive a call at 28 (± 3) days.

Patients who entered the study drug holiday will be scheduled to return to the clinic for a drug re-supply visit (see [Section 10.1.4.1](#)), and resumption of the full course of study treatment. Patients who entered the withdrawal sub-study after TV6 will be completed with the study after they return the questionnaires and undergo the DLco and spirometry assessment 4 to 5 weeks after completion of TV6, as described in [Section 10.1.3.9](#).

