11.2.4. PHQ-9

The PHQ-9 is the nine item self-report depression scale of the Patient Health Questionnaire which incorporates the nine diagnostic criteria for major depressive disorder in the DSM-IV (Diagnostic and Statistical Manual Fourth Edition). Patients are asked to rate the frequency of symptoms on a scale of 0 ("not at all") to 3 ("nearly every day"). The PHQ-9 is used to characterize affective and motivational states (apathy) in these patients.

The PHQ-9 will be completed in the ON state as indicated in the time and events tables in [Appendix 4](#) through [Appendix 10](#), including during the withdrawal assessment period at home.

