## Statistical Analysis Plan

- If the start day is missing, the first day of the month will be used.
- If the start day and month are missing, then the first day of the first month (January) will be used.

The original date and time will be shown on all listings of AEs. Listings will be provided for all AEs, serious AEs, AEs leading to study drug discontinuation, AEs leading to dose reduction, and deaths.

TEAEs will be summarized by SOC and PT for each treatment group and CVT-301 overall. TEAEs with onset after the treatment period are attributed to the treatment group during the treatment period. Both event and patient counts, where applicable, will be summarized. The counts will be complemented by percentages will be calculated for the patient counts unless otherwise specified. In addition, the incidence of TEAEs, normalized for duration of exposure to CVT-301 will be presented (number of TEAEs divided by the total exposure to CVT-301, measured as patient years).

- An overall summary of the number and percentage of patients reporting TEAEs and the number of TEAE events, drug-related TEAEs, severe TEAEs, serious TEAEs, TEAEs leading to dose interruption, TEAEs leading to study drug discontinuation, TEAEs leading to dose reduction and TEAEs leading to death
- TEAEs by SOC and PT, both as event and patient counts
- TEAEs by PT, both as event and patient counts
- Drug-related TEAEs by SOC and PT, both as event and patient counts
- Severe TEAEs by SOC and PT, both as event and patient counts
- Drug-related TEAEs by SOC, PT and severity, as event counts; percentages will be calculated for the event count out of total number of events
- Drug-related TEAEs by SOC, PT and relationship, as event counts; percentages will be calculated for the event count out of total number of events
- Serious TEAEs by SOC and PT, both as event and patient counts
- TEAEs leading to study drug interruption, both as event and patient counts
- TEAEs leading to study drug withdrawal, both as event and patient counts
- TEAEs leading to dose reduction, both as event and patient counts
- Most common AEs, both as event and patient counts, most common TEAEs is defined any AE preferred term occurred in greater than 10% total patients
- Time to first onset of most common AEs, classified as 0-1 months, >1-3 months, >3-6 months, >6-9 months and after 9 months, where the date of TEAE onset will be used as the time point for classification

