In 2016 the International Society for Central Nervous System Clinical Trials and Methodology (ISCTM) recommended a list of 41 adverse event terms for assessment of abuse potential ([Setnik 2016](#)). Subsequent to the Pre-NDA meeting the FDA also issued a new Final Guidance, FDA Guidance for Industry: [Assessment of Abuse Potential of Drugs](#) (January 2017) that included 19 adverse event terms for assessment of abuse potential. Therefore, based on the FDA recommendations and more recent publications, Acorda has modified its methodology for assessment of abuse potential based on the list of 213 adverse event terms published by [Love and Sun \(2013\)](#). Instead, Acorda is using a shorter more focused composite list of 73 adverse event terms including the 15 terms recommended by FDA in the CVT-301 FDA pre-NDA Meeting Minutes (October 2016), the 19 terms from the new FDA Guidance for Industry: [Assessment of Abuse Potential of Drugs](#) (January 2017) and the 41 terms recommended by ISCTM ([Setnik 2016](#)). Note, two terms (euphoria and drug withdrawal) are repeated in two of the lists. All of these terms except hedonistic hemostatic dysregulation have been converted into MedDRA, Version 19.0 Preferred Terms (PT). Because there was no MedDRA conversion term for the verbatim term hedonistic hemostatic dysregulation it was included in the composite list of 73 MedDRA terms. The MedDRA PT may provide abuse-related information about a drug, and

were used for assessment of abuse related adverse events in the CVT-301 clinical studies and Integrated Summary of Safety. The verbatim adverse event terms and MedDRA PT are provided in [Table 1](#).

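### No planned AE table separates events that start in the 28 days off CVT-301, so AE evidence on withdrawal or rebound is diluted among on-drug events

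*SAP*

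**What the plan says.** **How AEs are classified.** SAP 9.4 makes an AE treatment-emergent if it starts after the first CVT-301 dose following the relevant baseline. It gives no closing date. It then states that "TEAEs with onset after the treatment period are attributed to the treatment group during the treatment period". Time to first onset is tabulated in five classes counted from the start of treatment, and only for preferred terms seen in more than 10% of patients.

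**How withdrawal terms are searched.** The SAP section on abuse assessment methodology reports that FDA named withdrawal and rebound among the AE concepts of particular interest in Parkinson's patients. It says that "Acorda is using a shorter more focused composite list of 73 adverse event terms", drawn from three sources, and lists the resulting preferred terms under Table 1. The list includes "drug tolerance, drug withdrawal convulsions, drug withdrawal syndrome, elevated mood, emotional disorder" and "rebound psychosis, rebound tachycardia, sedation". No onset window is attached to it.

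**What is collected off drug.** Protocol 10.1.4 sets a 28-day withdrawal assessment after TV4, TV5 or TV6; 10.1.5 extends it to early withdrawals who have not yet had one. Sites telephone on Day 14 to remind patients about questionnaires and to "inquire about potential adverse events and changes in concomitant medications". A Day 28 call follows for those who enter after TV6. AEs are recorded at TV4.1/5.1 for those on the drug holiday (10.1.4.1).

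**What is analysed off drug.** SAP 8.1, 9.10, 9.14 and 9.15 summarise PHQ-9, Epworth, AWQ and DDS-PC as change from LDOT. SAP 9.9 gives C-SSRS as a shift from LDOT. SAP 9.16 gives MDS-UPDRS as values only.

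**The concern.** The sub-study exists to learn whether stopping CVT-301 produces withdrawal or rebound. AEs are one of its two sources of evidence, and the only one that carries seriousness, severity and causality. As planned, an AE that begins off drug sits in the same row as the same event begun on drug. A term such as agitation or mood swings may be captured by the search, but without a window it cannot be linked to stopping treatment. A real rise in the four off-drug weeks could pass unseen in the AE tables.

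The motor domain has the thinnest substitute. The MDS-UPDRS is first completed at home on Day 1 after the visit, while the clinic visits use the older UPDRS. The same instrument therefore has no LDOT value to compare with. Protocol 12.5 had foreseen change from baseline for UPDRS Parts 1 and 2 in this period.

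**Working it through.** **1. The plan's own figure.** The three sources give 15, 19 and 41 terms, and the SAP notes that "two terms (euphoria and drug withdrawal) are repeated in two of the lists". 15 + 19 + 41 - 2 = 73. A direct count of the preferred terms gives 73, all distinct. The figure reproduces.

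**2. What the 73 terms contain.**
- Seven contain the word withdrawal or rebound: drug withdrawal convulsions, drug withdrawal syndrome, withdrawal hypertension, withdrawal syndrome, rebound psychosis, rebound tachycardia and thought withdrawal. The last matches on the word only, which leaves six.
- The FDA guidance source includes a mood class ("inappropriate affect, somnolence, mood disorders and disturbances, psychosis"). The final list has five entries with mood in the name: elevated mood, euphoric mood, mood altered, mood swings and substance-induced mood disorder.
- No entry names depression, apathy, suicidality, akinesia, dyskinesia or tremor. Parkinsonism hyperpyrexia syndrome is the nearest motor entry.
- Several unlabelled entries could reflect withdrawal: agitation, irritability, emotional disorder, confusional state and neuroleptic malignant syndrome.

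**3. Is off-drug onset shown anywhere in the AE tables?** Tables 14.3.2.1 to 14.3.2.19 in SAP section 14 split AEs by treatment group, source study, severity, relationship, action taken and time from treatment start. None splits by on or off drug. Events after TV6 are pooled by the explicit sentence in SAP 9.4. Events in a holiday after TV4 or TV5 are pooled because the TEAE definition never closes.

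**4. Dilution.** Inputs: a 28-day window (protocol 10.1.4), and 56 treatment weeks (protocol section 7) or 52 (SAP 3.8).
- Off-drug share = 28 / (on-drug days + 28).
- Protocol: 56 x 7 = 392; 28 / 420 = 6.7%. The 420 days equal the 60 weeks at which a holiday patient reaches TV6.
- SAP: 52 x 7 = 364; 28 / 392 = 7.1%.
- For patients active in CVT-301-004, whose AEs count from that study, assume 12 more on-drug weeks (its last visit in the SAP section 8 table is Week 12): 28 / 504 = 5.6% or 28 / 476 = 5.9%.

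If the event rate off drug is RR times the on-drug rate, the pooled count rises by 28(RR - 1) / (on-drug days + 28):

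| RR (illustrative) | 56 weeks | 52 weeks |
|---|---|---|
| 2 | 6.7% | 7.1% |
| 3 | 13.3% | 14.3% |

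In the window itself, the same effects are a doubling or tripling.

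**The case against.** The strongest reply is that withdrawal was assigned to time-anchored questionnaires and not to the AE search. This largely stands. AWQ, DDS-PC, PHQ-9 and Epworth are compared with LDOT on nine days, C-SSRS has a shift from LDOT, and the protocol says "The PHQ-9 is used to characterize affective and motivational states (apathy) in these patients". A reader might infer that depression, apathy or suicidality after stopping is never examined as withdrawal, or that such AEs are lost. The documents do not support that: the questionnaires cover these domains, and SAP 9.4 lists all AEs with their original dates. Nor are events found only if labelled as withdrawal, as the unlabelled entries in step 2 show.

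The cover still has gaps. MDS-UPDRS has no change score. The C-SSRS text counts days after TV6, which does not fit a holiday after TV4 or TV5, and no indexed table shows its shift from LDOT. The PHQ-9 off-drug table uses the ITT set, which omits CVT-301-003 and CVT-301-009 patients.

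Second, a reader might call the 73-term list defective for lacking depression or motor terms. That does not follow. The list is an abuse-potential list built from FDA and ISCTM sources, and FDA asked for searches to use its terms. Extending it is a preference.

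Third, the abuse potential report and the integrated safety summary, which the SAP mentions but which are not available here, may hold an off-drug analysis. The finding is therefore limited to this SAP and its table index.

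Fourth, comparing off-drug with on-drug AEs is not clean. The AE question is put at about 14 days in the window, against visits about 12 weeks apart before TV4 and TV5 (with a call a week ahead). Nine rounds of home questionnaires may prompt reports, and oral PRN Parkinson's medication is permitted in the holiday. This stands, and it rules out a formal paired contrast.

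**Conclusion.** The point holds for AE tabulation. SAP 9.4 pools off-drug onsets with on-drug TEAEs, the term search has no time window, and no indexed AE table separates the two. The off-drug window is 6.7% of follow-up on the protocol's 56 weeks and 7.1% on the SAP's 52 (5.6% to 5.9% with 12 earlier active weeks), so a doubled rate moves the pooled count by roughly 6% to 7%. These shares assume that each patient contributes the full treatment period plus 28 days and that the background rate is constant. An early withdrawal is diluted less: stopping at week 12 gives 28 / (84 + 28) = 25%.

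Expected event counts cannot be given. The documents state no AE rate and no number of patients entering the window. The planned 290 are completers of the study, so a count built on them would rest on assumption.

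This does not touch the primary spirometry analysis. It is a modest gap in answering the sub-study's own question, and cheap to close.

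**What to change.** Add to SAP 9.4 one descriptive table of TEAEs by SOC and PT with onset on Days 1-28 after LDOT (TV4, TV5, TV6 or ET).

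- Denominator: the patients who entered the window, and their off-drug person-time. TV4.1/5.1 may fall up to a week after Day 28, so truncate at Day 28.
- Comparator: the same patients' on-drug rate, or their 28 days before LDOT, in the adjacent column. No formal paired test.
- Flag the Table 1 abuse and withdrawal terms, leaving out thought withdrawal. Keep the FDA/ISCTM-based list unchanged. Mood, apathy, suicidality and parkinsonism terms will appear in the ordinary SOC and PT rows.

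The cost is one table from AE onset dates and LDOT visit dates already collected. Its footnote should say that some events will be returning OFF time, that AE questioning and home questionnaires are more frequent off drug, that oral PRN Parkinson's medication is permitted then, and that counts may be sparse.
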